### **6.2. Schools selection and demographic census**

Before the start of the study, a serological survey will be conducted to select the schools. Blood samples will be collected from 20 randomly selected children from each school in Weoe for serological screening with Luminex. Only schools with sero-prevalence of 30-70% will be eligible for enrollment. Maximal number of selected schools will be 6-7, where 800 children will be individually randomized. Demographic census will be conducted during which name, date of birth/age, gender, village, hamlet, parents/guardian will be recorded (census form). Photograph will be taken from each participants to ensure the correct identification for treatment administration and follow up.

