### 8.3. Data analysis

*Plasmodium vivax* incidence is defined as the total number of new genetically distinct *P. vivax* clones per child per detected during the follow up period. The analysis will use the comparison of two incidence rates between SSAT group and control group. For comparison, data will be entered as the number of recurrent *Pv* (numerators) and the total length of time people contributed in the cohort (person-time) as denominators. We will calculate the exact probabilities (Fisher's and Mid-P), the rate ratio with the exact confidence intervals and the measures of the impact of intervention. We will report the 95% of confidence interval for this comparison. Measures of the impact of intervention are computed for the prevented fractions in the exposed and in the population and the preventable fraction in the population.

As secondary endpoints, we will use Kaplan-Meier method to detect differences in the time-to-first recurrence of *Pv* by PCR in SSAT and control arms. The log-rank test is used to detect any difference between the two groups. Cox proportion hazard will be used to measure the effect size.

Multiple recurrences of *P. vivax* infections will be calculated during follow up. Number of events will be calculated, divided by the total length of time people

contributed in the cohort (person-time) as denominators. We will calculate the exact probabilities, rate ratio with the exact confidence intervals, and the measures of the impact of intervention using same tests as above.

Symptomatic recurrent *P. vivax* is defined as LMF positive with fever ( $\geq 37.5^{\circ}\text{C}$ ) or history of fever in the last 3 days during follow up. The same statistical test will be performed to compare both groups.

Difference of seropositivity between the two arms before and after the intervention will be calculated using chi-square test with p value  $< 0.05$  as limit of significance.

Sensitivity, specificity, positive predictive value, and negative predictive value of POC *Pv* antibody rapid test will be reported with Luminex as the golden standard.

Type and number of AE and SAE will recorded, and reported with total length of time people contributed in the cohort (person-time) as denominators.

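### Section 8.3 applies exact pooled-rate tests to endpoints where one child can contribute several events, so p-values are too small and intervals too narrow whenever counts per child are overdispersed

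*Protocol*

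**What the plan says.** Section 8.3 of the protocol states that *P. vivax* "incidence is defined as the total number of new genetically distinct" clones found per child during follow-up. The next step enters the number of recurrences as numerator and "the total length of time people contributed in the cohort (person-time) as denominators". The test is fixed: exact Fisher and Mid-P probabilities, together with "the rate ratio with the exact confidence intervals and the measures of the impact of intervention". It adds: "We will report the 95% of confidence interval for this comparison".

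For multiple recurrences the section again pools: "Number of events will be calculated, divided by the total length of time people" spent in the cohort, "and the measures of the impact of intervention using same tests as above". Symptomatic recurrences are also to be compared by the same test. No per-child variance, robust error, random effect or overdispersion term is named for any of these.

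The protocol names the primary endpoint in two ways. The endpoint list in the synopsis and section 5.2 give the proportional reduction in incidence by PCR. The analysis row of the synopsis gives the proportion of children with a recurrence. The caption of Figure 3 (section 8.2) also refers to the proportion infected.

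**The concern.** An exact comparison of two pooled rates uses four numbers: the events and the person-time in each arm. Its variance comes from the Poisson assumption alone, so every event must be independent of every other. The protocol's own design makes that doubtful for the count endpoints:

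- Section 7.9 plans genotyping that separates clones within one infection, so a single positive sample can add several events.
- Section 6.3 plans monthly sampling for nine months, so one child can be counted repeatedly.
- Section 4 rests on the idea that some people carry hypnozoites and relapse while most carry none, so event rates differ between children.
- Section 6.2 points the same way: "Only schools with sero-prevalence of 30-70% will be eligible for enrollment". Within the enrolled schools, recent exposure will be mixed.

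Children are randomised individually, so the child is the independent unit. If counts vary more between children than a Poisson law allows, the pooled method understates the variance. An ineffective strategy would then be declared effective more often than 5% of the time, and the interval for the reduction would be too short.

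**Working it through.** **The plan's own figures.** The protocol gives no clones per infection, recurrences per child, dispersion or type I error. Its one related figure is power above 90% with 350 children per arm (section 8.2). The text states no effect size. If 20% is taken as the control proportion, 350 per arm gives 82% power for a 40% relative reduction and 91% for 45%; 90% is reached at about 44%. That is power for a per-child proportion and does not transfer to a clone count.

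**Formula.** Let E1 and E0 be the event totals and V the variance/mean ratio of counts per child.

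- The pooled method takes Var(log rate ratio) = 1/E1 + 1/E0.
- The true variance is about V × (1/E1 + 1/E0).
- Two-sided type I error = 2 × [1 − Φ(1.96/√V)].
- The interval on the log scale is too short by the factor √V, and its coverage is 1 minus the type I error.

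Two-sided 5% is inferred from the 95% interval, because no alpha is stated for this comparison.

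| Assumed V | 1.96/√V | Type I error | Interval should be wider by | Actual coverage |
|---|---|---|---|---|
| 1 | 1.96 | 5.0% | 1.00 | 95.0% |
| 1.2 | 1.79 | 7.4% | 1.10 | 92.6% |
| 1.5 | 1.60 | 11.0% | 1.22 | 89.0% |
| 2 | 1.39 | 16.6% | 1.41 | 83.4% |
| 3 | 1.13 | 25.8% | 1.73 | 74.2% |

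**What would produce such ratios.** All inputs below are assumptions. Null trials were simulated with 350 per arm and equal person-time, using the mid-P test.

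- *Several clones per infection, no difference between children.* V = E(C²)/E(C), where C is clones per infection. For C = 1 + Poisson(0.5), V = 2.75/1.5 = 1.83; simulated error 14 to 15%. For C = 1 + Poisson(1), V = 5/2 = 2.5; simulated 21%.
- *One clone, only a fraction f of children at risk, mean μ events per child.* V = 1 + (1 − f)μ/f. With f = 0.3 and μ = 0.5, V = 2.17; simulated 18%. With f = 0.7 and μ = 0.2, V = 1.09; simulated 6%.
- *20% of children infected once, 1 + Poisson(m) clones each.* V = E(C²)/E(C) − 0.2 × E(C). For m = 0.5, 1 and 2, V = 1.53, 2.10 and 3.07; simulated 11 to 12%, 17 to 18% and 26 to 27%. For m = 0.1 and 0.25, V = 0.97 and 1.20; simulated 4.8% and 6.4%. The 20% borrows the earlier PCR prevalence in section 8.2, which is not a nine-month infected proportion.
- *Rare symptomatic episodes.* Negative binomial counts with mean 0.05 to 0.1 and size 0.5 give V = 1.10 to 1.20; simulated 5.2% to 7.5%.
- *Each child counted once, 20% infected.* V = 1 − 0.2 = 0.8, so the error is 2 × [1 − Φ(2.19)] = 2.8%; simulated about 3%. The test is then conservative.

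**Does the remedy work?** In the scenarios with m = 0.5, 1 and 2, and with negative binomial counts of mean 1 and size 0.5, a child-level robust variance gave 4.7 to 5.5%. A negative binomial model with model-based variance, fitted for m = 0.5, 1 and 2, gave 4.5%, 2.6% and 1.0%, so it over-corrects there.

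**The case against.** The strongest objection is that the primary test may not be affected. The synopsis analysis row names the proportion of children with a recurrence, Figure 3 refers to that proportion, and section 8.3 lists multiple recurrences separately. With one outcome per child there is no inflation, and time to first recurrence is likewise unaffected. This stands as a limit on scope. It does not remove the point: section 8.3 defines incidence by clones, and the endpoint list and section 5.2 make incidence primary.

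A second objection is that the size is unknown. That also stands. A reader might infer that the false-positive rate is simply two to five times nominal. The documents do not support this. An error of 10% to 25% needs V between 1.42 and 2.90, and the protocol gives no such figure. Plausible inputs give anything from no inflation to more than five times.

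A third objection is that an SAP may refine the method. But the protocol names a specific test, and an SAP that followed it would inherit the problem.

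A reader might also fault the analysis for not adjusting for enrolment serostatus, or say that seronegative children dilute the effect. Neither follows. An unadjusted comparison is valid in an individually randomised trial, and the objective is the efficacy of the whole screening strategy, to which seronegative children belong. They also carry a treatment contrast of their own: at enrolment, asymptomatic children with *P. vivax* on microscopy are treated in the SSAT arm but not in the control arm (section 6.3). Nor is the school eligibility rule in section 6.2 an error; it only suggests that exposure varies.

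**Conclusion.** The point holds for every endpoint in section 8.3 that allows more than one event per child: clone-based incidence, multiple recurrences and, to a smaller degree, symptomatic recurrences. The stated method is valid only for independent Poisson events, and the protocol's sampling and genotyping make that unlikely. The direction is clear: under overdispersion, p-values are too small and intervals too narrow. The size is conditional: about 7%, 11%, 17% and 26% type I error at assumed variance/mean ratios of 1.2, 1.5, 2 and 3, and near 5 to 7% with little clustering or rare events. Whether the trial's main claim is exposed depends on which primary endpoint is meant. It is if a count of clones or recurrences is primary, and it is not if the proportion of children is primary.

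**What to change.** 1. For each endpoint that allows more than one event per child, replace the exact pooled-rate comparison with Poisson regression, log person-time as offset and child-level robust variance. A permutation test or bootstrap by child would also serve. If a negative binomial model is preferred, give it robust standard errors.
2. Keep the exact rate methods only for endpoints with at most one event per child.
3. State whether the numerator counts clones or recurrences.
4. Reconcile the synopsis endpoint list, section 5.2 and section 8.3 with the synopsis analysis row, so that one primary endpoint, count or proportion, is named throughout.

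The cost is a change of wording and a few lines of code, with no new data. Intervals for count endpoints will be wider, by about 1.1 to 1.7 times on the log scale at ratios of 1.2 to 3.

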	
standard finger stick microscopic.
 
 
• In the SSAT arm at enrollment, only children who are Pv seropositive and/or LMF Pv/Po positive receive supervised high-dose primaquine (1mg/kg for 7 days) regardless of their symptoms. All blood slides will be processed and read directly after blood collection. Then treatment will follow if positive. Sero-positive children, on the other hand, will commence treatment after the result is available (approximately 1 week). Symptomatic or asymptomatic LMF positive for Pf/Pm will be treated according to current national guidelines.
 
• In the control arm at enrollment, only children who are symptomatic and LMF Pv/Po positive will receive supervised high-dose primaquine (1mg/kg for 7 days).
 
• In both arms at every other timepoint, symptomatic LMF positive children will receive treatment in accordance with national guidelines (unsupervised).
 
• In both arms at the final timepoint, LMF will be conducted on all children and if positive will be treated according to national guidelines.
 
• As blood schizontocides, DHA-PP for 3 days will be given according to body weight (national guidelines).
 

Inclusion and Exclusion Criteria
	
Inclusion:
 
 
• resident of study area and attending selected elementary school in Grade 1-5
 
• no evidence of health condition that would interfere with study participation
 
• assent of child and documented parental informed consent
 
 
Exclusion:
 
 
• G6PD deficiency as determined by SD Biosensor quantitative determination of <70% G6PD activity (male: <4 U/g Hb, female: <6 U/g Hb).
 
• Haemoglobin < 9 g/dL
 

Analysis plan and sample size calculation
	
The study is designed to show a superiority of SSAT vs. routine care for the prevention of recurrent P. vivax infections. The primary study endpoint will be the proportion of children with recurrent P. vivax by PCR during 9 months of follow-up. Secondary endpoints include time-to-first P. vivax recurrence as well as incidence of symptomatic

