### 6.3. Study design and study overview

The study design is a randomized controlled trial with serological screening and treatment as the intervention. Selected schoolchildren will be allocated into two study arms: (1) serological screening and treatment (SSAT), and (2) routine care as control arm.

At enrolment, in the SSAT arm, individuals found *P. vivax* positive by either serological (Luminex) or Giemsa stained microscopic examination regardless of the symptoms will receive supervised treatment (direct observation) with high dose PQ (daily 1 mg/kg BW) for 7 days ( $P_o=P_v$ ). In the control arm, only symptomatic individuals found *P. vivax* positive by Giemsa stained microscopic examination will receive the same regimen ( $P_o=P_v$ ). In addition, in the treated children of both arms, dihydroartemisinin-piperaquine (DHA-PP) will be given as blood schizontocide according to body weight. All other species (*P. falciparum*, *P. malariae*) found by Giemsa stained microscopic examination will be treated according to national guideline. Serological examination will be performed by Luminex (done at Eijkman, Jakarta) and point-of-care (POC) antibody detection using rapid test on site

Follow up will be performed monthly for 9 months. During this period, 400  $\mu$ L of finger pricked blood samples will be collected from all children in both arms. These samples will be tested for malaria presence by PCR which will be done at EO CRU, Jakarta. However, children with clinical symptoms (body temperature of  $\geq 37.5^\circ\text{C}$  and/or history of fever within 3 days), will be examined by Giemsa stained microscopy on site, and treated if positive (any species) according to national guideline (unsupervised).

At the last follow up, a mass blood survey will be conducted to both arms for *Pv* serological test, LMF, and PCR. Those found positive by LMF for any species will be treated regardless of their symptoms.

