#### **7.9. Genotyping**

All samples from schoolchildren found to be qPCR-positive for *Plasmodium falciparum* or *Plasmodium vivax* will undergo genotyping using a targeted amplicon deep sequencing approach to genotype clones within individual infections, measure genetic relatedness, and discriminate new and existing infections. Each sample will undergo PCR-amplification of highly polymorphic genomic regions followed by next-generation sequencing (22,23).

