### **8.2. Sample size consideration**

Sample size is calculated based on the difference in the incidence of *P. vivax* infection between the intervention and control arm. The impact of the SSAT intervention is expected to reduce incidence of *P. vivax* in schoolchildren compared to control group. Our study in 2013 found *Pv* prevalence of ~20% by PCR (2). Different effect and sample sizes were simulated using a specific mathematical transmission model (24) and statistical power calculated. With the proposed sample size of 350 children per arm, we will have a power of >90% to detect a significant difference (Figure 3). Assuming 15% exclusion rate, we will recruit 400 children per arm.

**Figure 3. Simulation of various sample size (n=50-500) to detect significant difference in the proportion of infected subjects during follow up period.**

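### Time-to-first recurrence, the recurrence count and the synopsis primary have no rule excluding infections that persist from baseline, which stay untreated mainly in controls

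*Protocol*

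**What the plan says.** **Treatment at enrolment.** In the synopsis, SSAT children who are seropositive and/or slide-positive "receive supervised high-dose primaquine (1mg/kg for 7 days) regardless of their symptoms". For controls the rule is narrower: "In the control arm at enrollment, only children who are symptomatic and LMF" positive for P. vivax or P. ovale receive that regimen. Section 6.3 adds that "in the treated children of both arms, dihydroartemisinin-piperaquine (DHA-PP) will be given as blood schizontocide according to body weight".

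**Follow-up.** Section 6.3 collects blood monthly from every child in both arms, and "These samples will be tested for malaria presence by PCR". Under section 6.7, smears before the final visit are made only for children with symptoms, so an asymptomatic infection is not treated in either arm until month 9.

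**Event definitions.** In section 8.3, P. vivax incidence "is defined as the total number of new genetically distinct" clones per child. The paragraphs on time-to-first recurrence ("we will use Kaplan-Meier method to detect differences in the time-to-first recurrence of" P. vivax by PCR, with log-rank and Cox) and on multiple recurrences contain no clone condition, no requirement of a prior negative PCR and no restriction on baseline status. The analysis row of the synopsis gives the primary endpoint as the proportion of children with recurrent P. vivax by PCR, also without a clone condition.

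**Data available.** Section 7.9 genotypes every qPCR-positive schoolchild sample to "measure genetic relatedness, and discriminate new and existing infections". Appendix H schedules qPCR and genotyping at day 0 and at each follow-up visit.

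**The concern.** The stated objective is prevention of recurrent P. vivax, and the rationale is the hypnozoite reservoir. A control child who is PCR-positive without symptoms at enrolment keeps that infection. If it is still detectable at the first follow-up visit, the time-to-first analysis as written records an event at the earliest possible time. A comparable SSAT child who is seropositive or slide-positive has been given a blood schizontocide and is much less likely to produce that event. The arms can then separate even if SSAT prevents no relapse and no new infection. In the recurrence count, one untreated infection could be counted at several visits.

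This reaches beyond secondary endpoints. The synopsis makes the unprotected proportion the primary endpoint, and the caption of Figure 3 in section 8.2 describes the power simulation in terms of the proportion of infected subjects.

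**Working it through.** **Scale of the planned comparison.** The stated power above 90% with 350 per arm cannot be reproduced, because the readable text gives no effect size (Figure 3 is not shown). As a yardstick only: with 20% in controls, 350 per arm and a two-sided 5% test, 90% power needs about 11.1% in SSAT, a difference of 8.9 points.

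**Inputs from the protocol.** P. vivax PCR prevalence about 20% (section 8.2, a 2013 study); n = 350 per arm (section 8.2); monthly PCR for 9 months (section 6.3).

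**Assumptions, not in the protocol.**
- f, the share of baseline infections still PCR-positive at first follow-up: 25-75%. That visit is one month after the last primaquine dose (section 6.7). With about a week for serology and 7 days of treatment, it falls roughly six weeks after enrolment.
- r, the true nine-month risk, identical in both arms: 30%, varied over 20-40%.
- c, the share of SSAT carriers cleared: 90%, varied over 70-100%.
- All baseline carriers in controls untreated, which slightly overstates the effect.
- Two-sided 5% test.

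**Proportion endpoint.** With prevalence π:
- control = 1 - (1 - r)(1 - πf)
- SSAT = 1 - (1 - r)(1 - πf(1 - c))

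For π = 0.20, f = 0.25, r = 0.30, c = 0.90: control = 1 - 0.70 × 0.95 = 33.5%; SSAT = 1 - 0.70 × 0.995 = 30.35%.

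| π | f | Control | SSAT | Difference (points) | Apparent reduction | Test rejects |
|---|---|---|---|---|---|---|
| 20% | 25% | 33.5% | 30.35% | 3.15 | 9.4% | 14% |
| 20% | 50% | 37.0% | 30.7% | 6.3 | 17.0% | 42% |
| 20% | 75% | 40.5% | 31.05% | 9.45 | 23.3% | 74% |
| 10% | 25% | 31.75% | 30.2% | 1.6 | 5.0% | 7% |
| 10% | 75% | 35.25% | 30.5% | 4.7 | 13.4% | 27% |

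Every row has no true effect. At π = 20%, over r = 20-40% and c = 70-100%, the apparent reduction is 5-38% and the test rejects in 9-95% of trials.

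**Time-to-first endpoint.** A simulated log-rank test used 350 per arm, nine monthly visits and 600 runs per scenario. It assumed 90% of baseline infections asymptomatic, f = 25-75%, 60-90% of those infections treated in SSAT, and true recurrence of 10-40% in both arms. Persisting infections were counted as events at month 1; dropout and clustering were ignored.
- 20% prevalence: rate ratio 0.46-0.95; significant in favour of SSAT in 6-99% of trials.
- Middle case at 20% prevalence (f = 50%, 90% treated, 20% true recurrence): ratio 0.71, significant in 58%. The proportion endpoint in the same case is 27.2% vs 20.7%, and its test rejects in 52%.
- 10% prevalence: ratio 0.62-0.96; significant in 5-61%.
- Only new infections counted: two-sided rejection 3-7%, which is nominal within simulation error.

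**The case against.** **The main incidence measure is already protected.** A reader might infer that every PCR endpoint is biased, including the section 8.3 primary. The text does not support that: a persisting baseline clone that was detected is not new and so is not an event. The protection has gaps. A clone missed at baseline can later look new, and the same section then names the number of recurrent infections as the numerator. Even so, the definition addresses this problem directly.

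**Not every SSAT carrier is cleared.** PCR-positive children who are seronegative and slide-negative stay untreated in SSAT as well. The asymmetry concerns those positive on either test.

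**Clearance is part of the strategy.** DHA-PP belongs to the intervention, so fewer PCR-positive children is a real strategy effect. The fault lies in calling it prevented recurrence.

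**The size is uncertain.** The 20% is from 2013 and from another study, persistence has no source in the protocol, and schools are chosen on seroprevalence (section 6.2). One might also take the bias to be 18-53 persisting controls (350 × 0.20 × 0.25 to 0.75), or 5-15 points. That is a gross count: some of these children would become infected anyway, and a few SSAT carriers also persist.

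**Some of this belongs in an SAP.** Baseline adjustment and sensitivity analyses often go there, and their absence is not an error. What stands is that the protocol states its primary endpoint both with and without the clone rule, and leaves the rule off two further PCR endpoints.

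**The clone rule misses same-clone relapse.** Read literally, a baseline clone that is cleared and then returns is not counted. Section 8.3 does not say what new is measured against, so this is a limitation to manage and not a demonstrated error.

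**Conclusion.** The concern holds for three measures as written: time-to-first recurrence by PCR, the multiple-recurrence count and the synopsis version of the primary endpoint. Each can count infections persisting from baseline as recurrences, mainly in controls, and so favour SSAT with no relapse or new infection prevented. It does not hold in general for the section 8.3 incidence measure.

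For the proportion endpoint at 20% prevalence, 30% true risk and 90% clearance, the net spurious difference is about 3-9 points. At 10% prevalence it is about 1.6-4.7 points. These figures rest on the assumed persistence and the 2013 prevalence. They show that the bias could range from trivial to decisive; they do not predict its size in this cohort. The direction is clear, and the data needed to separate the two effects are already scheduled.

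**What to change.** (a) Reconcile the synopsis primary with section 8.3. Apply one event rule, identical in both arms, to every PCR recurrence endpoint: a positive counts only if it shows a clone not detected at baseline or in any earlier sample from that child. The rule should not depend on treatment received, because treatment differs by arm by design.

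(b) Adjust for, or stratify by, baseline qPCR status. Report the primary and time-to-first analyses in baseline PCR-negative children as a sensitivity analysis.

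(c) Report the any-PCR-positive comparison separately, labelled as the overall strategy effect (clearance plus prevention).

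**Cost.** Wording and analysis only; no new samples or visits. Rule (a) leaves out same-clone relapses, so add a sensitivity analysis that counts them under the same definition in both arms. Clones missed at baseline can still pass as new. The baseline-negative analysis uses fewer children: at 20% prevalence, about 280 of 350 per arm (350 × 0.80).

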### **5.2. Secondary objectives:**

1. To evaluate the performance of a point-of-care (POC) anti-*P. vivax* antibody detection test relative to Luminex (MagPix).
2. To evaluate safety of high dose PQ administration in schoolchildren.
3. To evaluate the accuracy of Sahli's method and Standard G6PD (SD Biosensor Inc., Deogyong-daero, Korea) relative to HemoCue for haemoglobin measurement.

4. To estimate the sensitivity and specificity of a microscopic diagnosis of blood by sample from skin (ankle) relative to standard finger stick microscopic and PCR.
5. To measure duration of gametocyte in the blood samples of the skin of the ankle and finger prick.
6. To estimate the sensitivity and specificity of magneto-optical hemozoin detection by Gazelle® (Hemex Health, USA) relative to standard finger stick microscopic and PCR. To analyse hemoglobinopathies in schoolchildren using HemeChip by Gazelle (Hemex Health, USA)

*Primary endpoint:* the proportional reduction of *P. vivax* incidence by PCR in children serologically screened relative to those receiving routine care during 9 months of active follow-up.

*Secondary endpoints:*

- (I) Difference in the time-to recur of *P. vivax* by PCR in SSAT and control arms.
- (II) Difference in the number of recurrent *P. vivax* by PCR in SSAT vs. control arms.
- (III) Difference in the incidence of recurrent symptomatic *P. vivax* by LMF in SSAT vs control arms.
- (IV) Seroconversion rate before and after intervention in SSAT and control arms.
- (V) Sensitivity and specificity of POC antibody detection test vs. gold standard Luminex assay.
- (VI) Adverse event (AE) and Severe Adverse Event (SAE) of high dose PQ in schoolchildren.
- (VII) Hb level in Sahli's method, Standard G6PD (SD Biosensor Inc., Deogyong-daero, Korea), and Gazelle® (Hemex Health, USA), in comparison with HemoCue (HemoCue AB, Angelholm, Sweden).
- (VIII) Sensitivity and specificity of microscopic examination to detect parasitemia from the shallow skin vasculature of the ankle (light microscopy-skin/LMS) compared to standard microscopic (light microscopy-finger/LMF) and PCR.

- (IX) Mean duration time of gametocyte in LMS and LMF
- (X) Sensitivity and specificity of magneto-optical hemozoin detection (MOD) compared to standard malaria detection and PCR.
- (XI) Sensitivity and specificity of Standard G6PD (SD Biosensor, Inc., Deogyong-daero, Korea Korea) compared to CareStart G6PD RDT (Access Bio. Inc., New Jersey, USA).

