### **6.9. Adverse Event (AE) and Serious Adverse Event (SAE)**

Adverse events (AE) are defined as any untoward and unintended reaction during the study period. AE will be identified and recorded in CRF by field team in collaboration with the teachers and primary health center attendants. These subjects will be given symptomatic treatment as necessary. Specific AE are black urine, gastro intestinal disturbances, blue lips and breathless.

Serious adverse events (SAE) is an AE which becomes serious and could endanger the life of subjects, cause hospitalization/prolong hospitalization, and disability to conduct normal life. The SAE will be recorded in SAE form and reported to PI, clinician coinvestigators, Ethic Committee, and DSMB within 24 hours. SAE' subjects will be treated in RSPP/RS Atambua until recover completely. Complete SAE report will be distributed within one month after the occurrence of SAE.

The observation of AE and SAE will be performed routinely according to the schedule of drug administration (7 days).

If subject is allergic to DHA-PP, second-line treatment (7 days quinine) will be provided by the team in close collaboration with local primary health center (11-17 kg: 3x1, 18-33 kg: 3x1½, 34-40 kg: 3x2). All treatments for AE/SAE which will be given either at the PHC or in hospital, should be reported to the investigator team and being documented in the database.

Treatment will be stopped immediately if any of these following occurs: 1) allergy to the antimalarial regimen being given, 2) Hb drop of more than 20%, 3) active hemolysis which is proven by urine test and Hb drop, 4) Hb drop with warning sign of MetHb (breathless, blue lip/cyanosis, drowsiness, lethargy, palpitation), 5) Any possible SAE related to antimalarial treatment. Hospitalisation is indicated for 2) to 5).

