**Table 3. Low dose Primaquine**

Single 0.25 mg/kg BW dose PQ will be given for *P. falciparum* or 14 days 0.25 mg/kg BW dose PQ for *P. vivax/P. ovale* infection any time during the study period.

Day	Species	Daily dosage based on body weight					
		≤ 5 kg	6-17 kg	18-30 kg	31-40 kg	41-59 kg	≥ 60 kg
1	P. falciparum	-	¼	½	¾	1	1
1-14	P. vivax/P. ovale	-	¼	½	¾	1	1

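### Section 8.3 divides adverse events by total cohort person-time, which does not estimate the risk of a 7-day high-dose primaquine course

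*Protocol*

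**What the plan says.** Section 5.2 makes the safety of high-dose primaquine in schoolchildren a secondary objective, and endpoint VI is "Adverse event (AE) and Severe Adverse Event (SAE) of high dose PQ in schoolchildren". Section 8.3 sets the analysis: "Type and number of AE and SAE will recorded, and reported with total length of time people contributed in the cohort (person-time) as denominators". The same section uses the same denominator for *P. vivax* recurrence over follow-up.

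Exposure is described elsewhere. At enrolment (6.3), SSAT children positive by serology or microscopy "will receive supervised treatment (direct observation) with high dose PQ (daily 1 mg/kg BW) for 7 days". In the control arm, only symptomatic microscopy-positive children get that regimen. Section 6.8 allows 10 days to complete the dose. After enrolment the Synopsis moves both arms to national-guideline treatment without supervision, for children who are symptomatic and microscopy-positive. Appendix B, Table 3 gives the low-dose 14-day primaquine regimen for a *P. vivax* or *P. ovale* "infection any time during the study period".

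On ascertainment, section 6.9 says "The observation of AE and SAE will be performed routinely according to the schedule of drug administration (7 days" (the bracket closes there). It also says "Adverse events (AE) are defined as any untoward and unintended reaction during the study period", and "All treatments for AE/SAE which will be given either at the PHC or in hospital, should be reported to the investigator team".

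**The concern.** A person-time denominator suits recurrence, because every child is at risk and sampled throughout follow-up. It does not suit a drug course of about a week. Most of the time that 8.3 puts in the denominator has no high-dose exposure and no routine adverse-event observation tied to that drug. Events per cohort person-year is then a different quantity from the risk of a course.

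Section 4 says the project should contribute evidence to guidelines for high-dose primaquine in primary health centres. Guideline users need to know how many treated children had an event during a course. Section 8.3 does not commit to giving events against the number treated, and it does not separate events under the high-dose course from events under later low-dose courses.

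**Working it through.** The protocol states no adverse-event rate, risk or precision, so there is no figure to reproduce. The check is person-time arithmetic.

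**Inputs**
- Course length: 7 days (6.3); completion window: 10 days (6.8).
- Follow-up: 9 months (6.3), with visits every 4 weeks according to the Synopsis lay summary. The first visit comes one month after the last primaquine dose (6.7), so the treatment week is added to the follow-up.
- School seroprevalence band: 30 to 70% (6.2). This is used only as an assumed range for the share of the SSAT arm treated.
- SSAT arm size: 350 (8.2).

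**Time per treated child, from first dose**
- Lower: 9 × 28 + 7 = 259 days.
- Upper: 0.75 × 365.25 + 7 = 280.9 days.

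**Share of that time on the course**
- 7 days: 7/259 = 2.7%; 7/280.9 = 2.5%. So 97.3 to 97.5% is unexposed to high-dose primaquine.
- 10 days: 10/259 = 3.9%; 10/280.9 = 3.6%.

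**Ratio of in-window rate to cohort rate**

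With *E*in events in the window, *E*out events after it, window *w* and total time *T* per treated child:

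ratio = (*T*/*w*) × *E*in/(*E*in + *E*out)

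| Window | All events in window | As many events after as in |
|---|---|---|
| 7 days | 259/7 = 37.0; 280.9/7 = 40.1 | 18.5; 20.1 |
| 10 days | 259/10 = 25.9; 280.9/10 = 28.1 | 13.0; 14.0 |

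These ratios count treated children only.

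**If untreated SSAT children are also counted**

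The rate is (share treated × risk per course)/time per child, so it moves in proportion to the share treated. As an illustration, assume a 20% risk of an event per course, one event per affected child, and 0.75 years of follow-up each. Person-time is 350 × 0.75 = 262.5 years.
- 30% treated: 350 × 0.30 = 105 children, 105 × 0.20 = 21 events, 21/262.5 = 8.0 per 100 person-years.
- 70% treated: 350 × 0.70 = 245 children, 245 × 0.20 = 49 events, 49/262.5 = 18.7 per 100 person-years.

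The ratio is 0.70/0.30 = 2.3 for an identical drug risk, whatever risk is assumed. The proportion among treated children is 20% in both cases, with exact (Clopper-Pearson) 95% confidence intervals of 12.8 to 28.9% (21/105) and 15.2 to 25.6% (49/245).

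**The case against.** The strongest reply is that little is lost. The sentence in 8.3 also promises the type and number of events, and the case report form in Appendix J records tablets taken and daily complaints. A reader given the number treated could work out the risk per course. No test, sample size or stopping rule uses the rate, and the daily haemoglobin and urine monitoring in 6.8 stands apart from it. A study-period rate also fits the definition of adverse events in 6.9. Correctly labelled, it answers another question and is not a miscalculation. All of this stands and lowers the weight of the point. It does not make the stated denominator answer endpoint VI.

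Four stronger readings are tempting, and the documents do not support them.

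- *Adverse events are watched for at enrolment only.* Section 6.9 ties routine observation to the dosing schedule and does not say enrolment only. It defines events over the study period and asks for PHC and hospital treatment to be reported. The case report form has columns to day 14, which would fit a low-dose course.
- *The schedule proves that ascertainment stops.* Appendix H has no adverse-event row even for the treatment week, so a missing row in the monthly columns shows nothing.
- *The 2.3-fold contrast is an error within this trial.* It compares two hypothetical trials at the limits of a school-eligibility band, and it applies only if untreated children are counted. Section 8.3 neither says so nor excludes it. Endpoint VI could be read as limiting the count to treated children.
- *The factor of 37 to 40 is a bias.* It is the ratio of two different quantities, and it shrinks if events are reported after the window.

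**Conclusion.** The point holds for the denominator. Section 8.3 fixes a rate that does not estimate the risk of a high-dose course. This is a rule the protocol states, not a detail it leaves open.

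The 37- to 40-fold gap (26- to 28-fold over 10 days) assumes that time runs from the first dose, that all counted events fall in the window, and that only treated children are counted. With as many events after the window as in it, the gap halves. Dependence on the share treated is conditional on untreated children being counted.

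The harm is limited to how one secondary endpoint is reported. A reader should not infer that safety events go unrecorded or that children are less protected. It is a minor-to-moderate flaw, worth correcting because the result is meant to inform guidelines.

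**What to change.** In 8.3, replace the cohort person-time denominator for adverse events with the following:

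- Among children who took at least one dose of high-dose primaquine, report the number and proportion with at least one AE and the number and proportion with at least one SAE, each with an exact 95% confidence interval.
- Count events from the first dose to day 10. This single window covers the completion period in 6.8. A day-7 limit would cut off children who are still dosing within the permitted time.
- If a rate is wanted as well, base it on person-days in that window.
- List later events, including those under low-dose courses, separately as counts.

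The cost is a short edit to 8.3. It needs no new samples, visits or staff, because tablets taken and daily complaints already have a place on the case report form, with columns to day 14.
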